3. STUDY PLAN

3.1. Study Design

Overall Design
This is an assessor-blinded (single), test site randomised, intra-subject comparison, repeated insult patch test to evaluate the skin irritation and sensitisation potential of a cosmetic facial product, under exaggerated conditions of use with controlled product application and under supervision of a dermatologist.
Day -14 to 0 / Visit 1 - Screening Visit
NOTE: Visit 1 and Visit 2 could be combined
The following assessments will be conducted: 
 1. Subject Informed Consent taken 2. Subject demographics collected 3. Medical history details 4. Details of current and concomitant medication collected 5. Fitzpatrick Skin Type Assessment (Appendix 3) 6. Inclusion/Exclusion criteria 7. Dermatologist determination for eligibility to participate in the study (including visual examination of the dorsum scapular region) 8. Subject eligibility
Days 1 to 22 / Visit 2 - Visit 14 - Induction Phase (3 Weeks)
NOTE: Visit 1 and Visit 2 could be combined

 GlaxoSmithKline	Document Name	Clinical Protocol 207587		
	Type	Version	Document Identifier	Effective Date
	eldo_clinical_doc	2.0; Most-Recent; Effective; CURRENT	090032d580d16e68	24-Mar-2017 07:31:59
	Reason For Issue	Auto Issue		

1. The following assessments will be conducted:
2. Continued eligibility check
3. Current/Concomitant Medications review
4. Inclusion/Exclusion criteria review (Inclusion criteria 3c (only) at Visit 2, if Visit 1 and 2 are not combined).
5. Dermatologist determination for continued eligibility to participate in the study (Visit 2/Day 1 only - if visits not combined)
6. Test Site Designation and Randomisation (Visit 2/Day 1 only)
7. Baseline grading/assessment of test sites (Per Appendix 2) (Visit 2/Day 1 only)
8. Patch applications (6 patch applications every Monday and Thursday, for 3 consecutive weeks).
9. Patch removal 24 (\pm 2) hours after application (Tuesday and Friday). Reaction grading/assessment performed by a qualified staff member (24 \pm 2 hours after application). Grading/assessments will be 30 minutes (up to 1 hour) after each patch removal (per Appendix 2)
10. Application site exposed to UVA irradiation.
11. **24 48** (\pm 2) hours after each UVA irradiation (or 72 (\pm 2) hours, in case of irradiation on Fridays), the sites will be evaluated for signs of dermatological reactions, according to Appendix 2.
12. Adverse event assessment

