3.4. Study Design and Application Amount Justification

Study Design:

This will be a single-center, randomised, assessor (single) blind study in healthy subjects aged 18 to 65 years. Subjects will be exposed to repeated insult dermal semi-occlusive patch application of a topical cosmetic formulation and negative control (saline solution).

Screening:

During screening subjects will sign an informed consent document and then a dermatological assessment will be conducted to ensure subjects have no dermatological conditions on their dorsum (backs) that might impact subject safety or study results and to ensure subjects have Fitzpatrick Phototype II to IV.

Each subject's medical history and medication history will be reviewed, as well as inclusion/exclusion criteria. After which, site staff will review lifestyle guidelines and directions with eligible subjects.

Induction Phase:

Visit 2/Day 1 of the Induction phase could be combined with Visit 1.

On Day 1 of the Induction Phase, eligible subjects will return to the study site and another dermatological assessment will be conducted to ensure continued eligibility (if Visits 1 and 2 are not combined) as well as review of concomitant medications since screening. The test site will be designated above the waist between the left scapula and the spinal mid-line. The sites within the patch of test product and negative control application will be randomly assigned and baseline grading/assessment of each test site will be performed.

 GlaxoSmithKline	Document Name	Clinical Protocol 207587		
	Type	Version	Document Identifier	Effective Date
	eldo_clinical_doc	2.0; Most-Recent; Effective; CURRENT	090032d580d16e68	24-Mar-2017 07:31:59
	Reason For Issue	Auto Issue		

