During the induction phase, there will be 6 patch applications (a patch will contain both the test product and saline solution) over 3 consecutive weeks, with each patch applied on Mondays and Thursdays. Each patch will remain in place for 24 (\pm 2) hours and then be removed, the treated areas will be cleaned with saline solution. After 30 minutes (maximum of 1 hour) the sites will be graded/evaluated as per the scale in Appendix 2. The patch test site will then be exposed to 5 J/cm² UVA radiation. The patch application site will be assessed pre-irradiation, following patch removal. Irradiation time depends on the power output of the light source and distance from the subject, and will be determined by the study site prior to UVA exposure. Irradiation will occur on the same days as patch removal (Tuesday and Fridays). Assessment of the irradiated sites will occur 48 hours (or 72 hours if the irradiation occurred on a Friday) after UVA exposure, prior to new patch application to the same site.

Rest Phase:

After the last grading/evaluation of the Induction Phase, subjects will enter a Rest Phase of 2 weeks. During this time there will be no product patch applications.

Challenge Phase:

After completing the Rest Phase, subjects will return for the Challenge Phase. Two naïve sites (previously un-patched, virgin areas) will be selected for the challenge patches both of these naïve areas will be graded/evaluated prior to any product application. Two patches, each with the test product and saline solution, will be randomly applied to each of the Challenge sites for 24 (\pm 2) hours, according to each subject's random assignment on Day 1 of the Induction phase. After 24 (\pm 2) hours, subjects will return for Challenge patch removal, the sites will be cleaned with saline solution and then graded/evaluated after 30 minutes (maximum of 1 hour). One of the Challenge patch sites will then be irradiated with 5 J/cm² of UVA radiation. Subjects will return 24 (\pm 2), 48 (\pm 2), and 72 (\pm 2) hours after patch removal for further grading/assessments of both the irradiated and non-irradiated Challenge sites.

End of Study:

After the Challenge phase is complete, a final clinical assessment by a qualified dermatologist will be performed to ensure that it is medically appropriate to exit each subject from the study. After all study assessments are completed, subjects will be discharged from the study site.

 GlaxoSmithKline	Document Name	Clinical Protocol 207587		

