5.3.1 Randomisation

A unique screening number will identify each subject screened for study participation. Screening numbers will be assigned in ascending numerical order as each subject signs their consent form. Subjects who meet all inclusion and exclusion criteria will be randomised according to the randomisation schedule. Randomisation numbers will be assigned in ascending numerical order as each subject is determined to be fully eligible. The randomisation number will be associated with the random location assignment of product to test site.

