6.2.1 Application of patches

The test product and saline solution (0.02 ml/cm² of each product) will be applied to a paper disc (or cell) contained within an adhesive patch. The number of cells available on the patch test tape can vary but in this study one will be used for test product and one for the reference; saline solution). The patch is then applied onto the dorsum (scapula region) of each subject for a period of 24 ± 2 hours, the sequence of the product application to the cells will be according to the randomisation schedule.

Induction Phase:

Visit 2/Day 1 of the induction phase could be combined with Visit 1.

On Day 1 of the Induction Phase, eligible subjects will return to the study site and another dermatological assessment will be conducted to ensure continued eligibility (if Visits 1 and 2 are not combined) as well as review of concomitant medications since screening. The test site will be designated above the waist between the left scapula and the spinal mid-line. The sites of test product and negative control application will be randomly assigned and baseline grading/assessment of each test site will be performed.

 GlaxoSmithKline	Document Name	Clinical Protocol 207587		
	Type	Version	Document Identifier	Effective Date
	eldo_clinical_doc	2.0; Most-Recent; Effective; CURRENT	090032d580d16e68	24-Mar-2017 07:31:59
	Reason For Issue	Auto Issue		

During the Induction phase, there will be 6 patch applications of both the test product and saline solution over 3 consecutive weeks, with each patch applied on Mondays and Thursdays. Each patch will remain in place for 24 (\pm 2) hours, then removed and the treated areas will be cleaned with saline solution. After 30 minutes (maximum of 1 hour) the site will be graded/evaluated as per the scale in Appendix 2. The patch test site will then be exposed to 5 J/cm² UVA radiation. The patch application site will be assessed pre-irradiation, following patch removal. Irradiation time depends on the power output of the light source and distance from the subject, and will be determined by the study site prior to UVA exposure. Irradiation will occur on the same days as patch removal (Tuesday and Fridays). Assessment of the irradiated sites will occur 48 hours (or 72 hours if the irradiation occurred on a Friday) after UVA exposure, prior to new patch application to the same site.

Rest Phase:

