6.2.2 Patch Assessments

An experienced trained assessor (s) will assess all the patch sites for the duration of the study according to the scoring scale in Appendix 2. Each patch will be removed and the treated areas will be cleaned with saline solution before visual assessment. Where ever possible, the same experienced trained assessor will perform all skin assessments for a given subject at each time point.

 GlaxoSmithKline	Document Name	Clinical Protocol 207587		
	Type	Version	Document Identifier	Effective Date
	eldo_clinical_doc	2.0; Most-Recent; Effective; CURRENT	090032d580d16e68	24-Mar-2017 07:31:59
	Reason For Issue	Auto Issue		

A Baseline patch site assessment will be carried out at Visit 2 (or Visit 1 if visits combined) prior to any patch application. Patch assessments will then be performed at Visits 3 to 13 for the Induction Phase (every 24 ± 2 hours following application, and 48 ± 2 (OR 72 ± 2 **IN CASE OF IRRADIATION ON FRIDAYS**) hours following patch site exposure to 5 J/cm^2 UVA radiation). After the last grading/evaluation in the Induction Phase at Visit 14, subjects will enter a Rest Phase of 2 weeks.

After completing the Rest Phase, subjects will return for the Challenge Phase (Visit 15). Each the naïve patch sites will be assessed prior to Challenge patch application. The 2 Challenge patches (with both the test and saline solution products) will be randomly applied to the Challenge site (previously untreated areas of skin) for 24 ± 2 hours. After Challenge patch removal at the study site (Visit 16), the patch site will be cleaned with saline solution and graded/evaluated after 30 minutes (maximum of 1 hour). One of challenge patch test site will then be exposed to 5 J/cm^2 UVA radiation. Subjects will return for further assessments after 24 ± 2 hours (Visit 17), 48 ± 2 hours (Visit 18) and 72 ± 2 hours (Visit 19) post patch removal for further grading/assessment of both the irradiated and non-irradiated Challenge sites.

Patch sites will be graded using a magnifying glass with a fluorescent daylight lamp. The assessor will be blinded to the treatment allocation.

The results will be presented as individual responses to each product at each assessment time point.

In any case of a positive reaction a dermatologist will be available to perform secondary assessments and grade the response with any further action as needed. This should occur the same day as the initial assessment performed by the trained assessor.

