ABDOMINAL PAIN	XX (XX.X)	XX	XX (XX.X)
DRY MOUTH	XX (XX.X)	XX	XX (XX.X)
VOMITTING	XX (XX.X)	XX	XX (XX.X)

N (%) = NUMBER (PERCENT) OF SUBJECTS NAE = NUMBER OF ADVERSE EVENTS.

PAGE X OF Y

PPD

PPD

PROTOCOL: 2075857

PROGRAM RUN DATE: DDMONYYYY

TABLE 14.3.1.2
SUMMARY OF TREATMENT EMERGENT ADVERSE EVENT BY SEVERITY

STUDY POPULATION: SAFETY POPULATION (N=XX)

SYSTEM ORGAN CLASS PREFERRED TERM	FACIAL MICELLAR CLEANSER (N=XX)						SALINE SOLUTION (N=XX)					
	MILD		MODERATE		SEVERE		MILD		MODERATE		SEVERE	
		N (%)	NAE	N (%)	NAE	N (%)	NAE	N (%)	NAE	N (%)	NAE	N (%)
NUMBER OF SUBJECTS WITH AT LEAST ONE AE	XX (XX.X)	XX	XX (XX.X)	XX	XX (XX.X)	XX	XX (XX.X)	XX	XX (XX.X)	XX	XX (XX.X)	XX
NUMBER OF SUBJECTS WITH NO AE	XX (XX.X)	XX	XX (XX.X)	XX	XX (XX.X)	XX	XX (XX.X)	XX	XX (XX.X)	XX	XX (XX.X)	XX
SKIN RELATED AES	XX (XX.X)	XX	XX (XX.X)	XX	XX (XX.X)	XX	XX (XX.X)	XX	XX (XX.X)	XX	XX (XX.X)	XX
SKIN AND SUBCUTANEOUS TISSUE DISORDERS	XX (XX.X)	XX	XX (XX.X)	XX	XX (XX.X)	XX	XX (XX.X)	XX	XX (XX.X)	XX	XX (XX.X)	XX
ERYTHEMA	XX (XX.X)	XX	XX (XX.X)	XX	XX (XX.X)	XX	XX (XX.X)	XX	XX (XX.X)	XX	XX (XX.X)	XX
DERMATITIS	XX (XX.X)	XX	XX (XX.X)	XX	XX (XX.X)	XX	XX (XX.X)	XX	XX (XX.X)	XX	XX (XX.X)	XX
NON SKIN RELATED AES	XX (XX.X)	XX	XX (XX.X)	XX	XX (XX.X)	XX	XX (XX.X)	XX	XX (XX.X)	XX	XX (XX.X)	XX
GASTROINTESTINAL SYSTEM	XX (XX.X)	XX	XX (XX.X)	XX	XX (XX.X)	XX	XX (XX.X)	XX	XX (XX.X)	XX	XX (XX.X)	XX
ABDOMINAL PAIN	XX (XX.X)	XX	XX (XX.X)	XX	XX (XX.X)	XX	XX (XX.X)	XX	XX (XX.X)	XX	XX (XX.X)	XX
DRY MOUTH	XX (XX.X)	XX	XX (XX.X)	XX	XX (XX.X)	XX	XX (XX.X)	XX	XX (XX.X)	XX	XX (XX.X)	XX
VOMITTING	XX (XX.X)	XX	XX (XX.X)	XX	XX (XX.X)	XX	XX (XX.X)	XX	XX (XX.X)	XX	XX (XX.X)	XX

N (%) = NUMBER (PERCENT) OF SUBJECTS NAE = NUMBER OF ADVERSE EVENTS.

PAGE X OF Y

PPD

PPD

PROTOCOL: 2075857

PROGRAM RUN DATE: DDMONYYYY

LISTING 16.1.7
RANDOMIZATION INFORMATION

STUDY POPULATION: RANDOMISED POPULATION (N=XX)

SUBJECT NUMBER	TREATMENT SEQUENCE [1]	RANDOMIZATION NUMBER	RANDOMIZATION DATE
PPD	PPD		DDMMYYYY

[1] A= FACIAL MICELLAR CLEANSER; B= SALINE SOLUTION

PAGE X OF Y

PPD

PPD

PROTOCOL: 207587

PROGRAM RUN DATE: DDMONYYYY

LISTING 16.2.1
INDIVIDUAL SUBJECTS PROTOCOL DEVIATIONS

STUDY POPULATION: RANDOMISED POPULATION (N=XX)

TREATMENT GROUP: SALINE SOLUTION

SUBJECT NUMBER	AGE/SEX/RACE[1]	VISIT #	DEVIATION SEQUENCE	PROTOCOL VIOLATION
PPD		VISIT 3	1	XXXXXXXXXXXXXXXXXXXXXXXXXXXX

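### As written, both Challenge patches reuse each subject's Day 1 cell order, so an unequal Induction reaction can carry an expectation into Challenge grading

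*Protocol*

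**What the plan says.** **Randomisation.** The study design lists in Protocol 3.1 and SAP 1.1 show one randomisation step, at Visit 2/Day 1, and none at Challenge. What is randomised is position within the patch. Protocol 3.4 states: "The sites within the patch of test product and negative control application will be randomly assigned". Protocol 6.2.1 uses one cell for the test product and one for saline, and says that "the sequence of the product application to the cells will be according to the randomisation schedule". Protocol 5.3.1 adds: "The randomisation number will be associated with the random location assignment of product to test site".

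**Application.** Induction patches return to the skin already used: Protocol 3.4 places each post-irradiation assessment "prior to new patch application to the same site". At Challenge, two patches go on unpatched skin, each holding both products. Protocol 3.4, 5.2 and 6.2.1 and SAP 1.3 all apply them "according to each subject's random assignment on Day 1 of the Induction phase". Protocol 6.2.2 says only that they are applied at random and does not name the assignment used.

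**Grading.** Protocol 5.3.2 requires the assessor to be blind to product allocation. Protocol 6.2.2 asks that, where feasible, "the same experienced trained assessor will perform all skin assessments for a given subject at each time point".

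**Records.** The template for SAP Listing 16.1.7 has one treatment-sequence column, one randomisation number and one date per subject, with A for cleanser and B for saline.

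Neither document provides a new cell order for Challenge, a separate Challenge assessor, or a rule that keeps earlier scores from the assessor.

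**The concern.** With two cells and a declared negative control in one of them, a reaction on one side only suggests which cell holds the product. If the cell order never changes, that inference still applies when the naïve Challenge sites are graded. It also links the two Challenge patches, because a reaction in one points to the same position in the other.

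Challenge is where photosensitisation is judged. Under Protocol 3.4, readings before irradiation and readings on the non-irradiated Challenge site inform primary irritation only. Photosensitisation therefore depends on the irradiated Challenge patch at Visits 17 to 19. Subjects who reacted in Induction are still challenged by default (Protocol 3.4 and 6.2.2), so the weakened blind falls on the subjects who say most about sensitisation. The results are descriptive, without formal inference (Protocol 9.3.2), so one or two subjects can shape the conclusion.

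**Working it through.** **1. Grading visits.** Protocol 3.4 gives 1 at baseline, 11 in Induction, 1 in Rest and 5 in Challenge: 1 + 11 + 1 + 5 = 18. This matches Visits 2 to 19 in the Schedule of Events.

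**2. Which visits a new Challenge order can protect.** Suppose the unequal reaction appears at Visit 3, the first post-patch grading. Visits 4 to 19 follow, which is 16 visits:
- Visits 4 to 14 (11 visits) grade Induction sites. The order is fixed there because patches return to the same skin.
- Visit 15 (1 visit) is graded before the Challenge patches go on.
- Visits 16 to 19 (4 visits) grade the Challenge patches.

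11 + 1 + 4 = 16, so the avoidable part is 4 visits. Three of these (17 to 19) come after irradiation.

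**3. How well the assessor could guess.** Let r be the probability that an unequal Induction reaction sits on the product cell. The documents give no value; assume 0.7 to 1.0, since saline is the negative control but its cell can also show UVA or patch effects.

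| Challenge order | Correct in one patch | Correct in both patches |
|---|---|---|
| Day 1 order reused | r = 0.7 to 1.0 | r = 0.7 to 1.0 |
| Independent order for each patch | 0.5 | 0.5 × 0.5 = 0.25 |

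Under reuse the two guesses are right or wrong together, so the joint probability stays at r.

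**4. How many subjects.** Let q be the share of subjects with an unequal Induction reaction (assumed). The expected number is n × q, and P(at least one) = 1 − (1 − q)^n. The sizes are from Protocol 9.1: at least 30 randomised and 25 evaluable.

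| q | n = 25: expected | n = 25: P(at least one) | n = 30: expected | n = 30: P(at least one) |
|---|---|---|---|---|
| 2% | 0.5 | 0.40 | 0.6 | 0.46 |
| 5% | 1.25 | 0.72 | 1.5 | 0.79 |
| 10% | 2.5 | 0.93 | 3.0 | 0.96 |
| 20% | 5.0 | 0.996 | 6.0 | 0.999 |

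**5. Illustrative bias.** Let b be the probability that an assessor with an expectation over-calls the expected cell (assumed 0.1 to 0.3). The net excess of subjects scored on the product is n × q × b × (2r − 1). With n = 25:
- Low end (q = 5%, b = 0.1, r = 0.8): 25 × 0.05 × 0.1 × 0.6 = 0.075 subjects.
- High end (q = 20%, b = 0.3, r = 1.0): 25 × 0.20 × 0.3 × 1.0 = 1.5 subjects.

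With independent Challenge orders, the part due to Induction expectation is 0. The formula covers over-calling only. An assessor who compensates by grading down would shift the result the other way, so the direction is not known.

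**The case against.** **The reuse is inferred.** The text pairs random application with the Day 1 assignment, and the randomisation schedule is not in the documents. It could hold separate Challenge orders fixed on Day 1. The sample row of Listing 16.1.7 is blacked out, so what a sequence encodes cannot be seen. This stands as a reason to ask the sponsor. However, one randomisation step, one location assignment per number and one sequence column point to a single order, and nothing in the text points to several.

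**Other safeguards exist.** A reader might infer that Challenge rests on a single visual grade, with the blind as its only protection. The documents do not support that. Each Challenge site is graded four times after patching, each patch has its own saline cell, and one patch is left non-irradiated. A dermatologist is available the same day to grade any positive reaction (Protocol 6.2.2). That check is partial: it follows a positive call, so it would not catch an under-call, and the trained examiner's interpretation is final.

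**The leak needs several conditions.** There must be an unequal reaction, the same assessor (asked for only where feasible), recall across a two-week rest or sight of earlier scores, and awareness that the order is reused. Protocol 3.4 also expects UVA erythema and pigmentation, so saline cells need not stay clear. All of this stands and limits the reach of the point.

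**A new order does not restore a full blind.** Once a one-sided Challenge reaction appears, the assessor can draw the same inference within that patch under any order. This is correct: the change removes the prior expectation and the link between patches, and no more.

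**The protocol intends a comparison across sites.** Its Introduction has the evaluator compare product alone, irradiated product and irradiated control. Different cell orders do not prevent this, because the comparison can be made from scores decoded by cell.

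**Conclusion.** The point holds in a limited form. On the natural reading, one Day 1 cell order is carried into both Challenge patches. In a subject with a one-sided or clearly unequal Induction reaction, the assessor can therefore expect the product in a known position at Visits 16 to 19, and can carry that expectation from one Challenge patch to the other.

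Two stronger readings do not follow. The whole study is not unblinded, since subjects without an unequal reaction give the assessor nothing to carry forward. Nor are all 16 visits after Visit 3 open to correction: 11 have an order fixed by same-site application, and one precedes Challenge patching.

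The size is unknown, because the documents give no reaction rate. The figures of 72% to 99.6% for at least one such subject, and about 0.08 to 1.5 excess subjects, rest on assumed values of q, r and b. The change is still worth making: the Challenge sites are naïve, so nothing requires the old order, and the blind is one that the protocol itself demands. No sample-size figure is affected.

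**What to change.** **Protocol 3.4, 5.2, 6.2.1 and 6.2.2, and SAP 1.3.** State that the cell order for each of the two Challenge patches is drawn independently of the Induction order and of the other Challenge patch, is held in the same pre-generated schedule, and is seen only by the person loading the cells. In the first three protocol sections and SAP 1.3 this replaces the reference to the Day 1 assignment; in 6.2.2 it fills the gap.

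**Grading.** State that scores from earlier visits are not shown to the assessor at Challenge grading.

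**SAP Listing 16.1.7.** Show three sequences per subject: Induction, Challenge patch 1 and Challenge patch 2.

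**If the schedule already holds separate Challenge orders,** say so, and correct the wording and the listing to match.

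**Cost.** Two more columns in the schedule and edits to four protocol sections, one SAP section and one listing. No extra visits, staff or subjects. The downside is a slightly higher risk of a cell-loading or decoding error. Record the cell position at each Challenge application to control it; the dispensing log in Protocol 5.4.1 serves product accountability and is not shown to capture cell position.
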